4.2 Secondary

- Identify new risk factors for Acute Kidney Injury (AKI)
- Understanding the incidence of AKI after cardiac surgery in Europe
- Validating a model for predicting discharge dialysis after cardiac surgery
- Investigate the performance of these models in specific surgeries: coronary surgery without cardiopulmonary bypass and heart transplantation.
- Assess the performance of other scales and compare them.
- Determine the prevalence and risk factors for Acute Kidney Disease (AKD) (renal injury beyond 7 days, up to 90 days).
- Determine the prevalence and risk factors for new Chronic Kidney Disease (CKD) (follow-up for 120 days or 4 months).
- Determine the prevalence and risk factors for CKD progression, defined by a one-stage progression in patients with pre-existing CKD. Follow-up for 120 days (4 months).

5. Methodology

5.1 Design: descriptive, observational, prospective, multicentre, prospective study.

5.2 Study population: patients undergoing cardiac surgery.

5.3 Ethical aspects: the study has been approved for assessment by the Ethical Committee for Research with Medicines of the Principality of Asturias.

5.4 Inclusion criteria: All patients over 18 years of age undergoing cardiac surgery.

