5.6 Study variables

Hospital

Age

Sex

Male

Female

Race

Asian

Black

Multiracial

White

Weight (kg)

Height(cm)

BMI

Comorbidities

- Hypertension
- Insulin-dependent diabetes
- Non-insulin-dependent diabetes
- Congestive heart failure
- Coronary artery disease
- Triple Vessel coronary artery disease
- Chronic obstructive pulmonary disease
- Poor mobility (musculoskeletal, neurological)
- Chronic kidney disease
- Peripheral vascular disease
- Atrial fibrillation
- Liver disease

NYHA (New York Heart Association Functional Classification)

Left ventricular ejection fraction (LVEF) %

Pulmonary systolic pressure (mmHg)

Unstable angina

Recent miocardial infarction (90 days)

Smoker YES/NO/Ex-smoker

Receives iSGLT2 (dapagliflozin, canagliflozin, empagliflozin...)

Receives GLP1 agonists (liraglutide, semaglutide, dulaglutide...)

Receives calcium antagonists (verapamil, nifedipine, amlodipine...)

Preoperative values

Serum creatinine (mg/dL)

FGe by Cockroft-Gault mL/min/1.73 m²

FGe by EPI CKD ml/min

eGFR by MDRD ml/min/

Serum Albumin (mg/dL)

Serum Urea (mg/dL) or Serum BUN (mg/dL)

Serum sodium (mmol/L)

Serum potassium (mmol/L)

Serum bicarbonate (mmol/L)

Haemoglobin (mg/dL)

Platelets

Bilirubin (mg/dL)

Surgery

On-pump CABG

Off-pump CABG

Valvular

Aortic

Combined (coronary+valvular)

Other, multiple procedures (>2)

Heart transplant

Previous heart surgery

YES/NO

Euroscore II

Classification Surgery

- Emergent
- Urgent
- Elective
- Salvage (pre-operative cardiopulmonary resuscitation)

Catheter to surgery

- Within 24 h
- >24 h this admission
- >24 h previous admission
- No catheter prior to surgery

Pre-operative critical status (IABP, mechanical ventilation, VT, CRP, amines, renal failure)

YES/NO

Endocarditis at the time of surgery

YES/NO

Preoperative cardiogenic shock

YES/NO

Use of IABP prior to surgery

YES/NO

Intraoperative variables

- CPB (cardiopulmonary bypass) time min
- Aorta cross-clamp time (min)
- Vasopressors YES/NO
- Inotropes YES/NO
- Red blood cell transfusion YES/NO

Number of red cell concentrates transfused
Platelet transfusion YES/NO
Fresh Frozen Plasma Transfusion YES/NO
Intraoperative diuresis (ml)
Nadir hemoglobin (lowest intraoperative in mg/dL)
Antibiotic (Gentamicin, Vancomycin, Cefazolin...)

Immediate postoperative values

Time from end of surgery to first analytical panel (hours)
Serum creatinine (mg/dL)
Serum albumin (mg/dL)
Urea (mg/dL) or BUN (mg/dL)
Serum sodium (mmol/L)

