Serum potassium (mmol/L)
Serum chlorine (mmol/L)
Serum bicarbonate (mmol/L)
Lactate (mmol/L)

Urgent re-intervention first 24h

YES/NO

Length of hospital stay (days)

Discharge status

Discharge

Éxitus

Need for dialysis at discharge

YES/NO

Postoperative renal failure

Creatinine at ICU admission

Creatinine at 24h

Creatinine at 48h

Creatinine at 72h

Peak creatine 4th to 7th day

Peak creatine 7th to 14th day

Last creatinine at hospital discharge

Does the patient develops Stage 1 AKI in the first 14 days?

*Stage 1 AKI: (\uparrow) Creatinine 1.5-1.9 times baseline or ≥ 0.3 mg/dL increase

If yes, which day?

Does the patient develops Stage 2 AKI in the first 14 days?

*Stage 2 AKI: (\uparrow) Creatinine 2-2.9 times baseline

If yes, which day?

Does the patient develops severe AKI in the first 14 days?

* Stage 3 AKI : (\uparrow) Creatinine ≥ 3 times baseline or ≥ 4 mg/dL increase or dialysis.

If yes, which day?

Does the patient requires renal replacement therapy within the first 14 days?

If yes, which day?

5.7 Sample size estimation: Taking into account an incidence of moderate severe AKI in Spain of 9% according to previous studies and using the

Wilcoxon test, 1045 patients are needed to detect a difference of 0.1 in aROC with a power of 80% and an alpha error of 0.05. Assuming a 10% loss to follow-up, 1150 patients would be needed.

5.8 Data collection: a data collection notebook will be used to carry out the study. The researcher will include in it the sample of patients, without any data that would allow their identification.

5.9 Analysis of results: the results will be analysed using the statistical package IBM-SPSS 20.0 for Mac OS and RStudio version 1.1.463. The basic statistics of centralisation and dispersion will be used to describe the results. For comparison of means, t-tests for independent data or Mann-Whitney U-tests will be used in those cases where the conditions for their application are violated. Chi-square tests shall be used for comparison of proportions. Bonferroni correction shall be applied for multiple contrasts. To study the predictive ability, 2 measures will be studied, the discrimination ability by means of the area under the ROC curve and the calibration by means of the Hosmer Lemeshow Test. The areas under the ROC curve will be compared using the Mann-Whitney U test.

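### Section 4.2 sets renal outcomes at up to 90 and 120 days, but section 5.6 lists no creatinine, dialysis or vital status after day 14 or hospital discharge, whichever is later

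*Combined protocol and SAP*

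**What the plan says.** Section 4.2 lists eight secondary objectives. Three of them look beyond the surgical admission:

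- AKD: "Determine the prevalence and risk factors for Acute Kidney Disease (AKD) (renal injury beyond 7 days, up to 90 days".
- New CKD: "Determine the prevalence and risk factors for new Chronic Kidney Disease (CKD) (follow-up for 120 days or 4 months".
- Progression of existing CKD: "CKD progression, defined by a one-stage progression in patients with pre-existing CKD. Follow-up for 120 days (4 months".

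Section 5.6 lists the study variables. The latest creatinine item with fixed days is "Peak creatine 7th to 14th day", followed by "Last creatinine at hospital discharge". AKI stages 1 to 3 are recorded over the first 14 days, as is renal replacement therapy: "Does the patient requires renal replacement therapy within the first 14 days". The only later dialysis item is "Need for dialysis at discharge", and survival is recorded only as status at discharge. Estimated GFR appears by three formulas, one of them "FGe by EPI CKD ml/min", all under preoperative values.

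Section 5.11 has the database completed when the sample size is reached, 6 to 12 months after ethics approval. Analysis is the next step, and no follow-up period is shown between them. Section 5.7 allows 10% for loss to follow-up but describes no follow-up contact.

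**The concern.** The objectives name horizons that the variable list does not reach. A site working from section 5.6 has no instruction to record anything about the kidney, or about survival, once the patient has gone home and day 14 has passed. The prevalence and risk-factor analyses for new CKD and for CKD progression would then have no dependent variable in nearly every patient, the exception being anyone still in hospital at day 120. AKD could be counted only if visible by day 14 or discharge. Later onset, and persistence or recovery up to day 90, would not be seen.

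Deaths after discharge matter as well. Without vital status, a patient who died before day 120 cannot be told apart from one who simply has no late creatinine.

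**Working it through.** The plan gives no figure to reproduce on this point. Its only number about follow-up is the inflation in section 5.7: 1045 × 1.10 = 1149.5, rounded to 1150. That carries no time horizon. The check is therefore a comparison of sections 4.2, 5.6 and 5.11, counting days from surgery (an assumption, since 4.2 does not state the origin).

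**Objectives against variables**

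| Objective (4.2) | Needed | Latest item in 5.6 | Result |
|---|---|---|---|
| AKD | Renal status from day 7 to day 90 | Day 7–14 peak; discharge creatinine | Observed to day 14 or discharge only |
| New CKD | Creatinine or eGFR, dialysis and survival at day 120 | Discharge creatinine, dialysis and status | No outcome if discharged before day 120 |
| CKD progression | CKD stage at baseline and at day 120 | Baseline side present; latest value at discharge | No outcome if discharged before day 120 |

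So 2 of 8 secondary objectives lack an outcome at their horizon and 1 of 8 is truncated.

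**Distance from the last listed value to the horizon**

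Let d be the day of discharge. The last listed value falls no later than max(14, d).

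- To day 90: 90 − max(14, d). For d ≤ 14 this is 90 − 14 = 76 days. For d = 30 it is 60 days.
- To day 120: 120 − max(14, d). For d ≤ 14 this is 120 − 14 = 106 days. For d = 30 it is 90 days.

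The day-30 discharge is an assumption, because the plan gives no expected length of stay.

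**Time available under section 5.11**

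120 days ÷ 30.44 days per month = 3.94 months. If the database closes when the last patient is entered, anyone enrolled in about the last 4 months has not reached day 120. If enrolment were uniform over the whole database step (an assumption):

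- 6-month step: 3.94 / 6 = 66% enrolled too late, 34% reach day 120.
- 12-month step: 3.94 / 12 = 33% enrolled too late, 67% reach day 120.

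Patients who do reach day 120 in time still have no listed field for the result.

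**The case against.** The strongest reply is that this is an omission from a list, not proof that the data will not be collected. Section 4.2 itself states the follow-up, section 5.6 does not claim to be exhaustive, section 5.8 refers to a data collection notebook that is not part of the document, and the 10% loss allowance suggests that some follow-up was intended. This is fair, and it limits the claim to the plan as printed. It does not remove the gap: section 5.6 is detailed down to the discharge creatinine, and nothing else in the document supplies a later value.

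Several stronger readings are tempting, and the documents do not support them.

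- A reader might infer from section 5.10, which mentions that patients in the database cannot be reviewed, that late values are irrecoverable. The wording may mean only that de-identified central records cannot be rechecked. Under section 8, sites confirm their own data before transfer, so they may well be able to obtain late values.
- A reader might set 120 days against the 2-month analysis step. Follow-up would not take place during analysis; the relevant step is database completion.
- A reader might conclude that nobody has time for follow-up. Only patients enrolled in about the last 4 months lack it.
- A reader might treat the uncovered days of the AKD window as a share of missed cases. The document gives no timing of AKD onset, so no such share can be derived.
- A reader might count the absence of postoperative eGFR as a separate gap. It can be derived from creatinine with age, sex, race and weight, all of which are listed. Late creatinine is what is missing.

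A further fair point concerns the remedy: one creatinine near day 90 does not measure AKD over the whole window. The fix allows for this.

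**Conclusion.** The concern holds for the plan as printed and should be fixed. Two of eight secondary objectives, new CKD and CKD progression, have no outcome at 120 days for patients discharged before then. A third, AKD, is truncated at day 14 or discharge, whichever is later. Section 5.11 adds a smaller problem for patients enrolled in about the last 4 months, assuming that the database closes once the sample size is reached.

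The conclusion rests on reading section 5.6 as the set of variables that sites will collect. If the notebook already holds later fields, the repair is to bring 5.6 and 5.11 into line with it. The external validation and model comparison in section 4.1 and the 14-day AKI outcomes are unaffected, so this is not a threat to the study's main purpose.

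**What to change.** **Preferred change**

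- In 5.6, add a dated creatinine, dialysis status and vital status near day 90 and again near day 120, each with a stated window.
- Derive eGFR and CKD stage with one named formula of the three already listed, the same at baseline and at day 120, so that a one-stage change cannot arise from switching formula.
- Because the notebook holds no identifying data (5.8), have each site extract these values from its routine records before its local coordinator confirms completeness (section 8).
- In 5.11, add about 4 months after the last patient for these outcomes only. The main analysis need not wait.
- Report the proportion of patients with a value at each time point, overall and by 14-day AKI status, and the number of deaths before each.
- Report the day-90 value as renal status near day 90, not as AKD prevalence over days 7 to 90. Episodes that arise and resolve between measurements stay unseen.

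**Fallback**

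If sites cannot supply these data, delete the two 120-day CKD objectives and restate AKD as renal injury from day 7 to day 14 or hospital discharge, whichever is later.

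**Cost**

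The preferred change means a few more fields per patient at sites that receive no funding (10.1, 10.2), possibly an ethics or consent amendment for data after discharge, and later reporting of these secondary outcomes. Late creatinine is probably measured more often in patients with renal injury, so prevalence among those with a value may be too high; reporting availability by AKI status shows this but does not correct it. The fallback needs only a text change, but gives up both CKD objectives and any AKD after day 14 or discharge.

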5.5 Exclusion criteria

- Exitus in the first 48h postoperative period
- Patient undergoing renal replacement therapy or preoperative dialysis
- Minor" cardiac surgery (sternal dehiscence, MCP removal or implantation, pericardial window)

5.6 Study variables

Hospital

Age

Sex

Male

Female

Race

Asian

Black

Multiracial

White

Weight (kg)

Height(cm)

BMI

Comorbidities

- Hypertension
- Insulin-dependent diabetes
- Non-insulin-dependent diabetes
- Congestive heart failure
- Coronary artery disease
- Triple Vessel coronary artery disease
- Chronic obstructive pulmonary disease
- Poor mobility (musculoskeletal, neurological)
- Chronic kidney disease
- Peripheral vascular disease
- Atrial fibrillation
- Liver disease

NYHA (New York Heart Association Functional Classification)

Left ventricular ejection fraction (LVEF) %

Pulmonary systolic pressure (mmHg)

Unstable angina

Recent miocardial infarction (90 days)

Smoker YES/NO/Ex-smoker

Receives iSGLT2 (dapagliflozin, canagliflozin, empagliflozin...)

Receives GLP1 agonists (liraglutide, semaglutide, dulaglutide...)

Receives calcium antagonists (verapamil, nifedipine, amlodipine...)

Preoperative values

Serum creatinine (mg/dL)

FGe by Cockroft-Gault mL/min/1.73 m²

FGe by EPI CKD ml/min

eGFR by MDRD ml/min/

Serum Albumin (mg/dL)

Serum Urea (mg/dL) or Serum BUN (mg/dL)

Serum sodium (mmol/L)

Serum potassium (mmol/L)

Serum bicarbonate (mmol/L)

Haemoglobin (mg/dL)

Platelets

Bilirubin (mg/dL)

Surgery

On-pump CABG

Off-pump CABG

Valvular

Aortic

Combined (coronary+valvular)

Other, multiple procedures (>2)

Heart transplant

Previous heart surgery

YES/NO

Euroscore II

Classification Surgery

- Emergent
- Urgent
- Elective
- Salvage (pre-operative cardiopulmonary resuscitation)

Catheter to surgery

- Within 24 h
- >24 h this admission
- >24 h previous admission
- No catheter prior to surgery

Pre-operative critical status (IABP, mechanical ventilation, VT, CRP, amines, renal failure)

YES/NO

Endocarditis at the time of surgery

YES/NO

Preoperative cardiogenic shock

YES/NO

Use of IABP prior to surgery

YES/NO

Intraoperative variables

- CPB (cardiopulmonary bypass) time min
- Aorta cross-clamp time (min)
- Vasopressors YES/NO
- Inotropes YES/NO
- Red blood cell transfusion YES/NO

Number of red cell concentrates transfused
Platelet transfusion YES/NO
Fresh Frozen Plasma Transfusion YES/NO
Intraoperative diuresis (ml)
Nadir hemoglobin (lowest intraoperative in mg/dL)
Antibiotic (Gentamicin, Vancomycin, Cefazolin...)

Immediate postoperative values

Time from end of surgery to first analytical panel (hours)
Serum creatinine (mg/dL)
Serum albumin (mg/dL)
Urea (mg/dL) or BUN (mg/dL)
Serum sodium (mmol/L)
Serum potassium (mmol/L)
Serum chlorine (mmol/L)
Serum bicarbonate (mmol/L)
Lactate (mmol/L)

Urgent re-intervention first 24h

YES/NO

Length of hospital stay (days)

Discharge status

Discharge

Éxitus

Need for dialysis at discharge

YES/NO

Postoperative renal failure

Creatinine at ICU admission

Creatinine at 24h

Creatinine at 48h

Creatinine at 72h

Peak creatine 4th to 7th day

Peak creatine 7th to 14th day

Last creatinine at hospital discharge

Does the patient develops Stage 1 AKI in the first 14 days?

*Stage 1 AKI: (\uparrow) Creatinine 1.5-1.9 times baseline or ≥ 0.3 mg/dL increase

If yes, which day?

Does the patient develops Stage 2 AKI in the first 14 days?

*Stage 2 AKI: (\uparrow) Creatinine 2-2.9 times baseline

If yes, which day?

Does the patient develops severe AKI in the first 14 days?

* Stage 3 AKI : (\uparrow) Creatinine ≥ 3 times baseline or ≥ 4 mg/dL increase or dialysis.

If yes, which day?

Does the patient requires renal replacement therapy within the first 14 days?

If yes, which day?

5.7 Sample size estimation: Taking into account an incidence of moderate severe AKI in Spain of 9% according to previous studies and using the

Wilcoxon test, 1045 patients are needed to detect a difference of 0.1 in aROC with a power of 80% and an alpha error of 0.05. Assuming a 10% loss to follow-up, 1150 patients would be needed.

5.8 Data collection: a data collection notebook will be used to carry out the study. The researcher will include in it the sample of patients, without any data that would allow their identification.

5.9 Analysis of results: the results will be analysed using the statistical package IBM-SPSS 20.0 for Mac OS and RStudio version 1.1.463. The basic statistics of centralisation and dispersion will be used to describe the results. For comparison of means, t-tests for independent data or Mann-Whitney U-tests will be used in those cases where the conditions for their application are violated. Chi-square tests shall be used for comparison of proportions. Bonferroni correction shall be applied for multiple contrasts. To study the predictive ability, 2 measures will be studied, the discrimination ability by means of the area under the ROC curve and the calibration by means of the Hosmer Lemeshow Test. The areas under the ROC curve will be compared using the Mann-Whitney U test.

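### Section 5.6 records intraoperative diuresis only as total mL with no duration of surgery, so urine flow (mL/kg/h) cannot be derived and its link with AKI may be masked

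*Combined protocol and SAP*

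**What the plan says.** Section 5.6 lists the item as "Intraoperative diuresis (ml" among the intraoperative variables. The operative times in the same list are "CPB (cardiopulmonary bypass) time min" and "Aorta cross-clamp time (min". One other item refers to the end of the operation, "Time from end of surgery to first analytical panel (hours", but it measures an interval after surgery. The list has no duration of surgery or anaesthesia, no start or end time and no urine collection period. Body weight in kg is listed, and off-pump coronary surgery is one of the procedure types.

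Section 4.2 includes the secondary objective "Identify new risk factors for Acute Kidney Injury (AKI" and, separately, the study of off-pump coronary surgery. For continuous variables section 5.9 says "For comparison of means, t-tests for independent data or Mann-Whitney U-tests will be used", with Bonferroni correction for multiple contrasts. It describes no normalisation of diuresis and no adjusted model. The AKI stages in section 5.6 use creatinine or dialysis, not urine output.

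**The concern.** Total volume is flow rate times weight times duration. Of these, the quantity with a plausible renal meaning is the flow rate. If long operations carry more AKI risk, they also give more time to collect urine. In a comparison of AKI with non-AKI patients, the duration effect then pushes volume up in the AKI group while low flow pushes it down, and the two offset each other.

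At stake is one candidate risk factor. A real effect of low urine flow may be missed. If flow has no effect, a high volume may be reported as a risk marker when it only reflects a long operation. Section 5.10 says that patients in the database cannot be reviewed, so a time that is not collected prospectively may be hard to recover.

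**Working it through.** **The plan's own figure.** Section 5.7 assumes an "incidence of moderate severe AKI in Spain of 9" per cent and states that "1045 patients are needed to detect a difference of 0.1 in aROC with a power of 80% and an alpha error of 0.05". The baseline AUC, the correlation between curves and the sidedness are not given, so 1045 cannot be reproduced uniquely. With the Hanley-McNeil variance, two-sided, and an assumed correlation of 0.3, the result is 1089 for 0.70 against 0.80 and 989 for 0.75 against 0.85, so 1045 is plausible. Then 1045 x 1.10 = 1149.5, the stated 1150, and 1150 x 0.90 = 1035 patients remain after the 10% loss. This point does not rest on that calculation; it uses only 1035 and 9%.

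**Unit check (assumed patients).** Flow = mL / (kg x h). For 600 mL at 60 kg:
- over 4 h: 600 / (60 x 4) = 2.50 mL/kg/h
- over 8 h: 600 / (60 x 8) = 1.25 mL/kg/h

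The listed variables give 600 / 60 = 10 mL/kg for both.

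**Inputs for the size of the effect.** None of these is in the documents; all are assumptions. Flow has median 1.5 mL/kg/h and CV 0.7, so its log-SD is sqrt(ln(1 + 0.49)) = 0.631. Duration is about 4.5 h with log-SD 0.28. Weight is 78 kg with log-SD 0.18. The three are independent. The log-odds of AKI change by -0.3 per SD of log flow and by b per SD of duration, with b = 0.2, 0.4 or 0.6.

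**Approximation.** The mean difference in log volume, AKI minus non-AKI, is about -0.3 x 0.631 + b x 0.28. The SD of log volume is sqrt(0.631² + 0.28² + 0.18²) = 0.714. With 0.09 x 1035 = 93 AKI cases and 942 others, the standard error of a standardised difference is sqrt(1/93 + 1/942) = 0.109.

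| b | Difference in log mL | In SDs | Power, approx. | Simulated power, total mL | Simulated power, mL/kg/h |
|---|---|---|---|---|---|
| 0.2 | -0.189 + 0.056 = -0.133 | -0.187 | 41% | 40% | 77% |
| 0.4 | -0.189 + 0.112 = -0.077 | -0.108 | 17% | 16% | 74% |
| 0.6 | -0.189 + 0.168 = -0.021 | -0.030 | 6% | 5% | 73% |

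The simulations use the Mann-Whitney test at 0.05. For mL/kg/h the standardised difference is -0.3 whatever b is, and the approximate power is 79%. Dividing by weight alone hardly helps: at b = 0.4, mL/kg gives 17%.

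**No effect of flow.** The difference is b x 0.28 / 0.714 = 0.078, 0.157 and 0.235 SD, with more urine in the AKI group. Total mL is then significant in 9%, 27% and 54% of simulated studies, against about 5% for mL/kg/h.

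**With the plan's Bonferroni rule.** The number of contrasts is not stated. For an assumed 40, the level is 0.05 / 40 = 0.00125. At b = 0.2, 0.4 and 0.6, power is 6%, 2% and 0% with total mL against 30%, 28% and 26% with mL/kg/h. False flagging of total mL is 1%, 3% and 10%.

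**Where the sign would change.** The difference is zero at b = 0.3 x 0.631 / 0.28 = 0.68 per SD. In a second set of assumptions (log-SD 0.5 for flow and 0.3 for duration, flow effect -0.4), the odds ratio per SD of total mL is 0.72, 0.83, 0.98 and 1.15 at b = 0, 0.3, 0.6 and 1.0.

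**Partial repair with bypass time.** Assume a correlation of 0.7 between CPB time and duration. Adjusting mL/kg for CPB time gives power of about 61%, 45% and 26 to 32% at the unadjusted level. False flagging with no flow effect is about 6%, 13% and 20 to 23%.

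**The case against.** The strongest reply has five parts.

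- **Weight is on the list.** This stands. A reader might infer that heavy patients distort the result beyond repair. They do not: in the second set of assumptions a weight effect of 0.3 per SD moves the odds ratio for total mL from 0.72 to 0.80, and dividing by weight gives 0.71.
- **CPB and cross-clamp times are recorded.** This stands in part. A reader might infer that no later model could help, but adjustment for CPB time recovers some of the loss in on-pump cases. It leaves residual confounding, section 5.9 does not plan it, and off-pump coronary surgery has no CPB time.
- **A real protective effect is masked, not reversed.** This stands for duration effects of 0.2 to 0.6. Reversal needs a stronger effect, and nothing in the documents supports one. The spurious positive link belongs to the case where flow has no effect.
- **Bonferroni shrinks both the false alarms and the gain from the fix.** This stands, which is why both sets of figures are given.
- **Diuresis is named in no objective, and the data collection notebook of section 5.8 is not in the documents.** Both are true. Its role as a candidate factor is inferred from the general objective in 4.2, section 5.9 does not rule out mL/kg, and the missing field is judged from the 5.6 list. If the notebook holds operative times, only the derivation rule is needed.

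**Conclusion.** The point holds as a minor one. From the variables in section 5.6, mL/kg/h cannot be derived. Existing data correct fully for weight and only partly for duration. If duration raises AKI risk by 0.2 to 0.6 log-odds per SD, power for a real flow effect is about 40% to 5% with total mL against about 75% with mL/kg/h. With Bonferroni for 40 contrasts it is about 6% to 0% against 26 to 30%, and false flagging of total mL is 1 to 10%.

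These sizes rest on assumed effects, spreads and independence of flow and duration; the documents give no figure for any of them and do not say that duration predicts AKI. A reader might extend the point to the validation of the score or to the outcome. The documents do not support that: the main objectives and the sample size do not depend on diuresis, and the AKI stages do not use it.

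**What to change.** Add one field to section 5.6, duration of surgery (min) or the urine collection period, and state in section 5.9 that intraoperative diuresis is analysed as mL/kg/h using the recorded weight. Where duration is missing, use mL/kg adjusted for CPB time where that exists, and do not interpret total mL as a risk factor. The cost is one more field per patient, one line of derivation, and retrieval of the time for patients already entered.

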The score developed by Demirjian et al has a good predictive ability for moderate to severe AKI after cardiac surgery in the European population.

4. Objectives

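### The Stage 3 clause on a 4 mg/dL creatinine rise adds no Stage 2-3 event at baselines up to 4.0 mg/dL; its intent and the stage cut-offs need settling

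*Combined protocol and SAP*

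**What the plan says.** The hypothesis (section 3) is that the score "has a good predictive ability for moderate to severe AKI after cardiac surgery in the European population". Section 5.6, under postoperative renal failure, holds the plan's only AKI definition:

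- Stage 1: "Creatinine 1.5-1.9 times baseline or ≥ 0.3 mg/dL increase"
- Stage 2: "Creatinine 2-2.9 times baseline"
- Stage 3: "Creatinine ≥ 3 times baseline or ≥ 4 mg/dL increase or dialysis"

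Stage 3 is the one labelled severe. No sentence maps moderate to severe onto stages; Stage 2 or 3 is the natural reading and is assumed here. Sites answer yes or no for each stage over 14 days and also record the creatinine values.

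The only renal exclusion in section 5.5 is "Patient undergoing renal replacement therapy or preoperative dialysis", so a raised baseline creatinine does not exclude a patient. Section 4.2 expects such patients: one secondary objective is CKD progression, "defined by a one-stage progression in patients with pre-existing CKD".

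**The concern.** The 4 mg/dL clause is the only absolute creatinine criterion above Stage 1. One would expect such a criterion to serve patients with a high baseline, in whom doubling demands a very large rise. Worded as an increase, it hardly does so for the combined Stage 2-3 endpoint. Across most of the range of raised baselines, that endpoint is governed by doubling or dialysis alone.

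This endpoint is the reference outcome for the discrimination and calibration of the AKI score and for its comparison with the other AKI models. If the sponsor meant a level reached, some patients with poor kidneys are counted as non-events, and a high predicted risk in them is scored as a false positive. All European hospitals with cardiac surgery are invited (section 1.9), so sites answering yes or no may also read the clause, and the gaps between the bands, differently.

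**Working it through.** **Inputs.** The stage rules and the recorded variables are in section 5.6, eligibility in section 5.5, and the 9% incidence and 1045 patients in section 5.7. Write b for baseline and p for peak creatinine (mg/dL), in a patient not dialysed. The plan states no figure on this point to reproduce.

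**Step 1: when the clause changes the stage (contiguous bands).**

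- Stage 3 alone: (b + 4)/b ≥ 3 if and only if b ≤ 2.0. The clause extends Stage 3 only above 2.0.
- Stage 2-3: without the clause, an event is p ≥ 2b. The clause adds a patient only if b + 4 ≤ p < 2b, which needs b > 4.0. On a 0.01 mg/dL grid the lowest baseline affected is 4.01.
- For contrast, the Stage 1 absolute clause extends Stage 1 whenever 0.3 < 0.5b, that is, b > 0.6.

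**Step 2: the peak needed to count as an event.** As written, it is the smaller of 2b and b + 4. If the clause meant reaching 4.0 with a rise of at least 0.3, it would be the smaller of 2b and the larger of 4.0 and b + 0.3.

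| b | 2b | b + 4 | As written | If a level |
|---|---|---|---|---|
| 1.0 | 2.0 | 5.0 | 2.0 | 2.0 |
| 2.0 | 4.0 | 6.0 | 4.0 | 4.0 |
| 2.5 | 5.0 | 6.5 | 5.0 | 4.0 |
| 3.0 | 6.0 | 7.0 | 6.0 | 4.0 |
| 3.5 | 7.0 | 7.5 | 7.0 | 4.0 |
| 4.0 | 8.0 | 8.0 | 8.0 | 4.3 |
| 5.0 | 10.0 | 9.0 | 9.0 | 5.3 |

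The two readings differ for every baseline above 2.0, with no upper limit.

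**Step 3: example.** From 2.5 to 4.5 the ratio is 4.5/2.5 = 1.8 and the rise is 2.0: Stage 1 as written, an event under the level reading.

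**Step 4: gaps between the printed bands.**

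- From 1.0 to 2.95 the ratio is 2.95 and the rise 1.95. Read literally this is above Stage 2, below Stage 3 and short of a 4 mg/dL rise, so only the 0.3 criterion applies and the patient is Stage 1. At a ratio of 2.95 this happens whenever 1.95b < 4, that is, b below about 2.05, so it concerns ordinary baselines.
- In the same gap the clause can create an event from just above 2.0: 2.10 to 6.12 has ratio 2.914 and rise 4.02. The 4.0 threshold in step 1 therefore assumes contiguous bands.
- From 2.5 to 4.9 the ratio is 1.96. A site that rounds to one decimal records 2.0 and Stage 2; one that does not records Stage 1.

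**Step 5: scale.** Expected events are 0.09 × 1045 = 94, so each reclassified patient changes the event count by 1/94, about 1.1%. How many there would be cannot be derived, because the documents give no baseline creatinine distribution.

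**The case against.** The strongest reply is that a redundant branch in an either-or rule is not an error. The clause says increase, in parallel with the Stage 1 wording, and section 2 cites KDIGO for management without giving staging criteria. The patient going from 2.5 to 4.5 is a non-event because Stage 2 is defined by a ratio; the clause does not make anyone a non-event. Changing the endpoint could also move it away from the outcome the score was built on, which the documents do not give. And since the creatinine values are collected, either reading can be derived at analysis.

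Most of this stands, and it limits the point. A reader might infer that patients with high baselines are misclassified; the documents support that only if a level was meant, which they do not say. Nor are such patients non-events as a class: those who double or are dialysed still count. Nor is every AUC and calibration result affected: need for dialysis at discharge is a separate variable with its own validation objective. A count of missed events would rest wholly on assumed shares, and no bias in an AUC has been shown. The clause is also not inert, because above 2.0 it moves patients from Stage 2 to Stage 3.

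The reply does not remove the arithmetic, the gaps in the bands, or the dependence on site answers. That the issue can be repaired from recorded values is a reason to write the rule down before analysis.

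**Conclusion.** The point holds as a defect of definition. With moderate to severe read as Stage 2-3 and contiguous bands, the 4 mg/dL clause adds events only at baselines above 4.0 mg/dL, so the main endpoint has almost no working absolute criterion although non-dialysed CKD patients are eligible. The documents do not establish whether this was intended, so it should be put to the sponsor as a question of intent and not as a proven misclassification. The band gaps need no such assumption: on the printed text, a ratio of 2.95 with a rise under 4 mg/dL and no dialysis is only Stage 1. The number of patients and the effect on AUC or calibration are unknown and may be small. The change is worth making because it is cheap and concerns the reference outcome of the main objective.

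**What to change.** 1. State in section 5.6 that moderate to severe AKI means Stage 2 or 3, if that is the intent. Reconcile the 4 mg/dL clause with the staging definition the study means to use and with the outcome on which the score was developed.
2. If a level was meant, word it as creatinine reaching ≥ 4.0 mg/dL together with at least the Stage 1 rise. If a rise was meant, say so and report the level reading as a sensitivity analysis.
3. Replace the printed bands with continuous cut-offs: ≥ 1.5, ≥ 2.0 and ≥ 3.0 times baseline, naming the preoperative creatinine as baseline.
4. Derive every stage centrally from the recorded preoperative and postoperative creatinine values and the 14-day RRT field. Keep the site yes/no answers as a cross-check; they remain useful because the values up to 72 h are fixed-time readings and not peaks.

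Cost: one line of definition and a derivation script, with no new measurement. Incidence may change slightly from the 9% assumed in section 5.7.
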